5.3.5. Patient Reported Outcomes

For the HAQ-DI, SF-36, WPAI, EuroQol EQ-5D and the FACIT-Fatigue, rules suggested by the producers of these will be followed in calculating the values. If these rules are not enough for imputing a value, then the value is missing.

NRI approach (see [Section 5.3.3](#)) will be used to impute the missing data of HAQ-DI response (ie, decrease of at least 0.22).

6. ANALYSES AND SUMMARIES

6.1. Primary Endpoint(s)

6.1.1. Change in DAS28-4 (ESR) Score from Randomization (at Week 24) to the End of Double-Blind MTX Withdrawal Phase (at Week 48)

6.1.1.1. Primary Analysis

- Analysis time points: Week 48
- Analysis population: FAS-DB
- Analysis methodology: Change from randomization (at Week 24) will be analyzed using the MMRM (specified in [Section 5.2.2](#)).
- Covariate: Baseline of DAS28-4(ESR) and prior use of a bDMARD.
- Imputation for missing values: Observed data will be included in the MMRM model, the missing values will be handled in the model, where the values are assumed to be missing at random.
- Supporting objective and Decision rule: Primary Objective, upper bound of 95% CI of treatment difference < 0.6.

Reporting results:

- Raw data: The sample size, mean, standard deviation, median, minimum and maximum at randomization (Week 24) and post-randomization visits will be presented for each treatment arm.
- Change from randomization: The sample size, mean, standard deviation, median, minimum and maximum will be presented for each treatment arm. The LS means, 95% confidence interval for the LS means, difference between the LS means between treatment groups and the corresponding 95% CI, p-value will be presented.

Figures

- Line plots of the LS means (+/-SE) at Weeks 48 and 36 for two treatment groups.
- Plot of 95% CI of the LS mean difference between treatment groups at Weeks 48 and 36.

6.1.1.2. Sensitivity/Robustness Analyses

To support the interpretation of the primary analysis the following analyses will be performed:

6.1.1.2.1. Analysis for PPAS

- Dependent Variable: Change in the DAS28-4(ESR) from Week 24 to Week 48
- Analysis time points: Week 48
- Analysis population: PPAS
- Analysis methodology: Change from Week 24 will be analyzed using the MMRM (specified in [Section 5.2.2](#)).
- Covariate: Baseline of DAS28-4(ESR) and prior use of a bDMARD.
- Imputation for missing values: Observed data will be included in the MMRM model, the missing values will be handled in the model, where the values are assumed to be missing at random.
- Supporting objective and Decision rule: Primary Objective, upper bound of 95% CI of treatment difference <0.6.

Reporting results:

- Raw data: The sample size, mean, standard deviation, median, minimum and maximum at randomization (Week 24) and post-randomization visits will be presented for each treatment arm.

- Change from randomization: The sample size, mean, standard deviation, median, minimum and maximum will be presented for each treatment arm. The LS means, 95% confidence interval for the LS means, difference between the LS means between treatment groups, the corresponding 95% CI and p-value will be presented.

Figures

- Line plots of the LS means (+/-SE) at Weeks 48 and 36 for two treatment groups.
- Plot of 95% CI of the LS mean difference between treatment groups at Weeks 48 and 36.

6.1.1.2.2. Multiple Imputations

- Dependence Variable: Change in the DAS28-4(ESR) from Week 24 to Week 48
- Analysis population: FAS-DB
- Analysis time point: Week 48
- Analysis methodology: Change from Week 24 will be analyzed using the MMRM (specified in [Section 5.2.2](#)).
- Covariate: Baseline of DAS28-4(ESR) and prior use of a biological DMARD
- Imputation for missing values: multiple imputation (see [Section 5.3](#)).

Reporting results:

- Change from Week 24: The LS means, 95% confidence interval for the LS means, difference between the LS means between treatment groups and the corresponding 95% CI will be presented.
- Plot of 95% CI of the LS mean difference between treatment groups at Weeks 48 and 36.

6.2. Secondary Endpoint(s) and Other Endpoints in the Double-Blind Phase

6.2.1. Change in the DAS28-4(ESR) from Week 24 to Week 36

All analyses performed for Week 48 will be performed for Week 36. See [Section 6.1.1](#).

6.2.2. Changes in the DAS28-4 (CRP) from Week 24 to Week 48 and from Week 24 to Week 36

- Analysis time points: Week 48 and Week 36
- Analysis population: FAS-DB
- Analysis methodology: Change from Week 24 will be analyzed using the MMRM (specified in [Section 5.2.2](#)).
- Covariate: Baseline of DAS28-4(CRP) and prior use of a bDMARD

- Imputation for missing values: observed data will be included in the MMRM model, the missing values will be handled in the model, where the values are assumed to be missing at random.

Reporting results:

- Raw data: The sample size, mean, standard deviation, median, minimum and maximum at randomization (Week 24) and post-randomization visits will be presented for each treatment arm.
- Change from Week 24: The sample size, mean, standard deviation, median, minimum and maximum will be presented for each treatment arm. The LS means, 95% confidence interval for the LS means, difference between the LS means between treatment groups, the corresponding 95% CI and p-value will be presented.

Figures

- Line plots of the LS means (+/-SE) at Weeks 48 and 36 for two treatment groups.
- Plot of 95% CI of the LS mean difference between treatment groups at Weeks 48 and 36.

6.2.3. Other Continuous Endpoints in the Double-Blind Phase

The same analysis in [Section 6.2.2](#) will be performed for changes from Week 24 to Week 48 and from Week 24 to Week 36 in the:

- CDAI;
- SDAI;
- Tender/painful joint counts;
- Swollen joint counts;
- Subject assessment of arthritis pain VAS;
- Subject global assessment of arthritis;
- Physician global assessment of arthritis;
- CRP;
- HAQ-DI;
- SF-36 (8 domain scores and 2 component scores);
- WPAI;
- EuroQol EQ-5D;
- FACIT-Fatigue scale score;

- RAPID3 (US and Canada ONLY).

6.2.4. LDA as assessed by DAS28-4(ESR) \leq 3.2 at Weeks 48 and 36

- Analysis time points: Week 48 and Week 36;
- Analysis population: FAS-DB;
- Analysis methodology: normal approximation (specified in [Section 5.2.1](#));
- Imputation for missing values: NRI ([Section 5.3.3](#)), observed cases.

Reporting results:

- The sample size, frequency and percentage of responders at post-randomization visits will be presented for each treatment arm difference between treatment groups and the corresponding 95% CI and p-value will be presented.

Figures

- Line plots of the percentage (+/-SE) at Weeks 48 and 36 for two treatment groups.

6.2.5. Other Binary Endpoints in the Double-Blind Phase

The same analysis in [Section 6.2.4](#) will be performed at Weeks 48 and 36 for

- LDA as assessed by DAS28-4(CRP) \leq 3.2;
- LDA as assessed CDAI \leq 10;
- LDA as assessed SDAI \leq 11;
- Remission as assessed by ACR-EULAR Boolean remission criteria;
- Remission as assessed by DAS28-4 (ESR) $<$ 2.6;
- Remission as assessed by DAS28-4 (CRP) $<$ 2.6;
- Remission as assessed by CDAI \leq 2.8;
- Remission as assessed by SDAI \leq 3.3;
- HAQ-DI response (ie, decrease of at least 0.22).

6.2.6. ACR 20, 50, 70 at Weeks 48 and 36

- Analysis time points: Week 48 and Week 36;
- Analysis population: FAS-DB;
- Analysis methodology: normal approximation (specified in [Section 5.2.1](#));
- Imputation for missing values: NRI ([Section 5.3.4](#)), observed cases

Reporting results:

- The sample size, frequency and percentage of responders at post-randomization visits will be presented for each treatment arm difference between treatment groups and the corresponding 95% CI and p-value will be presented.

Figures

- Line plots of the percentage (+/-SE) at Weeks 48 and 36 for two treatment groups.

6.3. Other Endpoint(s)

6.3.1. Changes in DAS28-4 (ESR) from Day 1 to Week 12 and from Day 1 to Week 24

- Analysis time points: Week 12 and Week 24
- Analysis population: FAS-OL
- Analysis methodology: descriptive summary.
- Imputation for missing values: no imputation.

Reporting results:

- Raw data: The sample size, mean, standard deviation, median, minimum and maximum at baseline will be presented.
- Change from Day 1: The sample size, mean, standard deviation, median, minimum and maximum will be presented.

6.3.2. Other Continuous Endpoints in Open-Label Run-in Phase

The same analysis in [Section 6.3.1](#) will be performed for changes from Day 1 to Week 12 and from Day 1 to Week 24 in the

- DAS28-4 (CRP);
- CDAI;
- SDAI;
- Tender/painful joint counts;
- Swollen joint counts;
- Subject assessment of arthritis pain VAS;
- Subject global assessment of arthritis;
- Physician global assessment of arthritis;
- CRP;
- HAQ-DI;

- SF-36 (8 domain scores and 2 component scores);
- WPAI;
- EuroQol EQ-5D;
- FACIT-Fatigue scale score;
- RAPID3 (US ONLY).

6.3.3. LDA as assessed by DAS28-4(ESR) \leq 3.2 at Weeks 12 and 24

- Analysis time points: Week 12 and Week 24;
- Analysis population: FAS-OL;
- Analysis methodology: descriptive summary;
- Imputation for missing values: NRI ([Section 5.3.3](#)), observed cases.

Reporting results:

- The sample size, frequency, percentage of responders, and 95% CI of percentage will be presented.

6.3.4. Other Binary Endpoint in Open-Label Run-in Phase

The same analysis in [Section 6.3.3](#) will be performed at Weeks 12 and 24 for

- LDA as assessed by DAS28-4(CRP) \leq 3.2
- LDA as assessed CDAI \leq 10
- LDA as assessed SDAI \leq 11
- Remission as assessed by ACR-EULAR Boolean remission criteria
- Remission as assessed by DAS28-4 (ESR) $<$ 2.6
- Remission as assessed by DAS28-4 (CRP) $<$ 2.6
- Remission as assessed by CDAI \leq 2.8
- Remission as assessed by SDAI \leq 3.3
- HAQ-DI response (ie, decrease of at least 0.22)

6.3.5. ACR 20, 50, and 70 at Weeks 12 and 24

- Analysis time points: Week 12 and Week 24
- Analysis population: FAS-OL
- Analysis methodology: descriptive summary.

- Imputation for missing values: NRI ([Section 5.3.4](#)).

Reporting results:

- The sample size, frequency, percentage of responders and 95% CI of percentage will be presented.

6.4. Exploratory Endpoints

See [Section 6.2.3](#) and [Section 6.3.2](#) for the analysis of exploratory endpoint RAPID3.

6.5. Subset Analyses

To check the consistency of the primary endpoint across subgroups, change from randomization at Week 48 and Week 36 will be analyzed for below subgroups:

- Age group: 18-45, 46-64, ≥ 65 ;
- Geographic region: US, Europe, Latin America, Rest of the World;
- Race: White, Black, Asian, Other;
- Prior bDMARD: Yes, No;
- Disease severity: Moderate (DAS28-4 (ESR) ≥ 3.2 and ≤ 5.1), Severe (DAS28-4 (ESR) > 5.1).

Each subgroup factor along with its 2-way and 3-way interactions with treatment group and visit will be added to the MMRM model without imputation for missing data described in [Section 5.2.2](#), and outputs from this augmented model will be used for comparisons within each subgroup.

6.6. Baseline and Other Summaries and Analyses

6.6.1. Baseline Summaries

Demographic and baseline characteristics will be summarized for FAS-OL and FAS-DB according to Pfizer data standards.

6.6.2. Study Conduct and Subject Disposition

Subjects evaluation, disposition, discontinuation will be summarized for FAS-OL and FAS-DB according to Pfizer data standards.

6.6.3. Study Treatment Exposure

Treatment duration and number of subjects by treatment duration category will be summarized for FAS-OL and FAS-DB according to Pfizer data standards.

6.6.4. Concomitant Medications and Non-Drug Treatments

Prior drug and non-drug treatment for RA, concomitant drug and non-drug treatment for RA for FAS-OL and FAS-DB according to Pfizer data standards.

6.7. Safety Summaries and Analyses

6.7.1. Adverse Events

Adverse events will be summarized according to Pfizer data standards for each phase.

- TEAEs;
- Serious AEs;
- Serious infections;
- Adjudicated events.

AEs will not be double counted across phases. Counting of AEs will be based on start date of AE. If the start date of an AE is in the open-label phase, the end date of the AE in the double-blind phase and severity of AE remained the same or became lower in both phases, then the AE will be counted in open-label phase, not in the double-blind phase. However, if the same AE started in the open-label phase, and get worse in severity in the double-blind phase, then the AE will be counted in both phases.

In all these analyses attention will be restricted to assessments that occurred no more than 28 calendar days after the last dose of study drug.

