7.2. Assessment of New Physical Findings

At all other visits (Visits 2-5), an abbreviated physical examination will be performed assessing the following: weight, vital signs, skin examination including careful examination for melanoma and non-melanoma skin cancer, lungs, heart, lower extremities for peripheral edema, abdomen and lymph nodes. Any clinically significant changes from the last complete physical examination should be recorded as AEs; ongoing AEs should be updated, as appropriate.

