8.9. Severity Assessment

If required on the AE CRFs, the investigator will use the adjectives MILD, MODERATE, or SEVERE to describe the maximum intensity of the AE. For purposes of consistency, these intensity grades are defined as follows:	
MILD	Does not interfere with subject's usual function.
MODERATE	Interferes to some extent with subject's usual function.
SEVERE	Interferes significantly with subject's usual function.

Note the distinction between the severity and the seriousness of an AE. A severe event is not necessarily an SAE. For example, a headache may be severe (interferes significantly with the subject's usual function) but would not be classified as serious unless it met one of the criteria for SAEs, listed above.

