3.6. Safety Endpoints

3.6.1. Adverse Events

- *All adverse events (AEs), including serious adverse events (SAEs).*
- Adjudicated safety events

An AE is considered treatment emergent relative to a given treatment if:

- the event occurs for the first time during the effective duration of treatment and was not seen prior to the start of treatment, or
- the event was seen prior to the start of treatment but increased in severity during treatment.

The effective duration of treatment is determined by the lag time. Any event occurring within 28 days, whether this occurs during a break in treatment or at the end of treatment, is attributed to the corresponding treatment period.

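### SAP 6.7.1 has no rule for a run-in adverse event that first becomes serious after randomization at unchanged severity, so the double-blind serious-event tables omit it

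*SAP*

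**What the plan says.** SAP 6.7.1 names four AE summaries to be produced for each phase: treatment-emergent AEs, serious AEs, serious infections and adjudicated events. One set of counting rules follows, and it applies to all four:

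- The general rule: "Counting of AEs will be based on start date of AE".
- An AE that starts in the run-in and ends in the double-blind phase without a rise in grade: "then the AE will be counted in open-label phase, not in the double-blind phase".
- The only exception is a rise in grade: "if the same AE started in the open-label phase, and get worse in severity in the double-blind phase, then the AE will be counted in" each of the two.

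SAP 3.6.1 uses the same kind of test for treatment emergence of a pre-existing event: "the event was seen prior to the start of treatment but increased in severity during treatment".

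Protocol 8.9 asks the investigator, if the CRF requires it, to grade AEs "to describe the maximum intensity of the AE", and adds a caution: "A severe event is not necessarily an SAE". Protocol 8.1 allows an event first reported as non-serious to be classed as serious later. Protocol 8.5 defines a serious infection by hospitalization for treatment, parenteral antimicrobial therapy or another seriousness criterion, not by grade. Protocol 9.5 splits all safety displays by phase.

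**The concern.** Comparing the safety of monotherapy with that of continued MTX is a secondary objective (Protocol 2.1.2). Only the double-blind phase contains both arms, so an event informs that comparison only if it reaches the double-blind tables.

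For an AE already present at randomization, the SAP admits it on one ground, a higher severity grade. Becoming serious is a different change. It can happen at the same grade, for instance when a moderate infection leads to admission or parenteral treatment. Such a change happens under the randomized regimen, but the rule books it to the open-label run-in, where there is no comparator. The tables most exposed are those for serious AEs and serious infections, where counts are usually low and one or two events can change the picture.

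**Working it through.** The plan states no figure on this point, so there is nothing to reproduce. The check applies the SAP 6.7.1 rule to constructed records. All have an AE that starts in the run-in, continues past randomization on Day 168 (assumed also to be the first double-blind dose) and ends in the double-blind phase.

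| Case | Severity after Day 168 | Seriousness | Phase under SAP 6.7.1 |
|---|---|---|---|
| A | same or lower | never serious | run-in only |
| B | higher | never serious | both phases |
| C | higher | first serious after Day 168 | both phases |
| D | same or lower | first serious after Day 168 | run-in only |

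A and B behave as intended. C reaches the double-blind tables because the grade rose, provided the rise is captured; the SAP does not say whether its run-in entry would also be shown as serious. D is the gap.

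**A worked record for case D.** An infection starts on Day 160 at moderate severity. The subject is randomized on Day 168; the only condition in Protocol 4.3 is CDAI-defined low disease activity. On Day 175 the subject is hospitalized for the infection, still graded moderate.

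1. Protocol 8.5: it is a serious infection from Day 175.
2. SAP 6.7.1: the start date is in the run-in and the grade did not rise. It is counted as a run-in serious infection only.
3. SAP 3.6.1: it was present before the double-blind phase and did not increase in severity, so the treatment-emergence definition does not bring it back.
4. Protocol 7.23 and 8.5: the subject is withdrawn, with the serious AE given as the reason on the CRF.
5. SAP 6.6.2: discontinuations are summarized for FAS-DB, which includes this subject.

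Steps 2 and 5 conflict. The double-blind disposition table shows a discontinuation for a serious AE, while the double-blind serious AE table has no such event for that subject.

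**Size.** The documents give neither the share of subjects with an AE ongoing at randomization nor the share of those AEs that turn serious at unchanged grade. As an illustration on assumed rates:

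subjects affected = 232 × (share with an ongoing AE) × (share of those turning serious at unchanged grade)

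- 232 × 0.10 × 0.02 = 0.46
- 232 × 0.40 × 0.02 = 1.86
- 232 × 0.10 × 0.05 = 1.16
- 232 × 0.40 × 0.05 = 4.64

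That is about 0.5 to 5 subjects in all, or 0.2 to 2.3 per arm of 116. The 232 is the planned minimum number randomized (Protocol 9.1); the counts scale with the number actually randomized.

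**The case against.** The strongest reply is that the case is narrow and may be handled elsewhere. A serious event often rises in grade too, and then the existing exception applies. SAP 6.7.1 refers to sponsor data standards that are not in the documents, and Protocol 8.15.2 describes a separate form for serious AEs, which might carry its own date. The event does not vanish from the report, because it appears in the run-in table and the withdrawal appears in the FAS-DB disposition. No safety hypothesis or decision rule depends on these counts; the only formal test in SAP 5.1 is the efficacy one.

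Much of this stands, and it limits the size of the point. It does not remove it. The SAP states its own phase rule, keyed to AE start date and severity, and names no other date for the serious tables. A separate form does not help unless the SAP says its date is used. Appearing in the run-in table is the misassignment itself, since that table cannot compare the arms.

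**Conclusion.** The point holds on the text of the two documents. A run-in AE that first meets a seriousness criterion (or, for serious infections, the parenteral-treatment criterion) after the first double-blind dose, at the same or lower severity, is left out of the double-blind serious AE and serious infection summaries. The number is unknown and probably small; the illustration above rests wholly on assumed rates. The loss can occur in either arm and its direction cannot be predicted. The primary efficacy conclusion does not depend on it.

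A reader might infer something stronger: that worsening in severity after randomization is also lost, because Protocol 8.9 describes only a maximum intensity and Protocol 7.2 says "ongoing AEs should be updated, as appropriate". On that reading an event that went from mild in the run-in to severe afterwards could not be told from one that was severe throughout. The documents do not establish this. The SAP says that worsened AEs count in both phases. Severity collection in 8.9 is conditional on a CRF that is not provided. Section 7.2 concerns the abbreviated physical examination at Visits 2 to 5 and does not bar a new record when an event worsens. How severity is captured by phase is therefore a detail to confirm, not a demonstrated loss of events. Nor does every event that turns serious stay in the run-in: case C above is re-counted if its rise in grade is recorded.

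**What to change.** Change SAP 6.7.1 before unblinding:

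1. Count a run-in AE in the double-blind phase if, after the first double-blind dose, it either worsens in severity or first becomes serious.
2. In the serious AE and serious infection tables, assign the event to the phase in which the seriousness criterion (or, for serious infections, the parenteral-treatment criterion) was first met, whether or not severity changed. Use the date the criterion was met, not the date of reporting or reclassification.

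The cost is two SAP sentences and the matching programming, with no added visits or subjects. The date on which the criterion was first met must be available, so check that the serious AE form or CRF holds it. One episode can then appear in the AE tables of both phases, so each subject should be counted once per phase.

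As a secondary clarification, confirm in the CRF completion guidance that severity before and after the first double-blind dose can be recovered, for example through a linked new record on worsening. If it already can, a sentence in the SAP saying so is enough.

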4.4.2. Vaccine and Exposure to Infections Guidelines

It is recommended that subjects be up to date on all recommended vaccination (including pneumococcal vaccine and flu vaccine) per local practice guideline prior to enrollment.

Vaccination with live components is prohibited within the 4 weeks prior to first dose of investigational product to 6 weeks after last dose of investigational product. In addition, current routine household contact with children and others who have been vaccinated with live vaccine components may pose a risk during treatment and for 6 weeks following completion of the study. Some of these vaccines include adenovirus Type 4 & Type 7, BCG, Dengue Fever, measles, mumps, rubella, varicella (“chickenpox”) vaccine or varicella-zoster vaccine, oral polio vaccine, rotavirus, Yellow Fever and the intranasal (inhaled) flu vaccine.

Following vaccination with live component vaccines, the virus may be shed in bodily fluids, including stool, and there is a potential risk that the virus may be transmitted. General guidelines for immunosuppressed subjects suggest that household contact with children and others who have been vaccinated with live vaccine components should be avoided following their vaccination with the following vaccines for the stated time period:

- Attenuated typhoid fever vaccination for 4 weeks following vaccination;
- Oral polio vaccination for 6 weeks following vaccination;
- Attenuated rotavirus vaccine for 10 days following vaccination;
- FluMist[®] (intranasal flu vaccine) for 1 week following vaccination.

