6.2.8. Telephone Follow-up (At least 28 days following last dose of study drugs)

This visit should occur at least 28 days following the last dose of study drugs. This visit can be combined with the End of Study visit as long as it occurs at least 28 days following the last dose of study drugs. If it is not combined with the End of Study visit, this visit can be performed over the phone. There is a +14 day window for the telephone follow-up.

- AE assessment.
- Pregnancy status.

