8.2. Reporting Period

For SAEs, the active reporting period to Pfizer or its designated representative begins from the time that the subject provides informed consent, which is obtained prior to the subject's participation in the study, ie, prior to undergoing any study-related procedure and/or receiving investigational product, through and including 28 calendar days after the last administration of the investigational product. SAEs occurring to a subject after the active reporting period has ended should be reported to the sponsor if the investigator becomes aware of them; at a minimum, all SAEs that the investigator believes have at least a reasonable possibility of being related to investigational product are to be reported to the sponsor.

AEs (serious and non-serious) should be recorded on the case report form (CRF) from the time the subject has taken at least 1 dose of investigational product through the subject's last visit.

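### SAP 6.7.1 cuts adverse events off by assessment date and SAP 3.6.1 by event date; read literally, 14 of the 15 permitted follow-up call days miss the cut-off

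*SAP*

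**What the plan says.** SAP 6.7.1 lists the summaries to be produced by phase: treatment-emergent events, serious events, serious infections and adjudicated events. Its closing sentence covers all of them: "attention will be restricted to assessments that occurred no more than 28 calendar days after the last dose of study drug".

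Earlier in the same section, in the paragraph on not counting an event twice across phases, the SAP says: "Counting of AEs will be based on start date of AE".

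SAP 3.6.1 sets the lag that makes an event treatment-emergent. It credits to the preceding treatment the events it describes as follows: "Any event occurring within 28 days, whether this occurs during a break in treatment or at the end of treatment".

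Protocol 6.2.8 sets the telephone follow-up, whose tasks are an adverse-event assessment and a check of pregnancy status. On timing it says "This visit should occur at least 28 days following the last dose of study drugs", and then "There is a +14 day window for the telephone follow-up". It adds: "This visit can be combined with the End of Study visit as long as it occurs at least 28 days" after the last dose.

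Protocol 8.2 sets the active reporting period for serious events as running "through and including 28 calendar days after the last administration of the investigational product".

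**The concern.** Two SAP rules use the same number of days but attach it to different dates. SAP 3.6.1 asks when the event happened. SAP 6.7.1, as worded, asks when it was assessed. They agree when an event is assessed soon after it starts. They part when an event starts inside the 28 days and is first recorded after them, and the telephone follow-up is timed so that this can easily happen.

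Evaluating safety and tolerability is a secondary objective. Protocol 1.2.1 names serious infections, herpes zoster and malignancy among the potentially important risks. Two programmers working from this SAP could produce different adverse-event tables from the same data, and the one who follows 6.7.1 word for word would leave out events that 3.6.1 assigns to treatment.

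**Working it through.** The plan states no figure to reproduce here. The check intersects two timing rules.

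**Inputs**
- Earliest follow-up contact: Day 28 after the last dose (Protocol 6.2.8).
- Window: +14 days (Protocol 6.2.8 and Schedule of Activities).
- Literal cut-off: assessment on or before post-dose Day 28 (SAP 6.7.1).
- Treatment-emergent lag: event on or before post-dose Day 28 (SAP 3.6.1).

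**Permitted call days**
- Last permitted day: 28 + 14 = 42.
- Number of permitted days: 42 − 28 + 1 = 15.
- Days meeting the literal cut-off: Day 28 only, so 1/15 = 6.7%.
- Days failing it: Days 29 to 42, so 14/15 = 93.3%.

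Merging the call with the End of Study visit does not change this count, because a merged visit must also be at least 28 days after the last dose.

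**One event under both rules.** Take an infection that starts on post-dose Day 10 and is first reported at a call on Day 35.
- SAP 3.6.1: 10 ≤ 28, so it falls within the lag period.
- SAP 6.7.1 read literally: 35 > 28, so it is excluded.

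**All combinations of onset day and call day**
- Onset on Days 1 to 28 with a call on Days 28 to 42: 28 × 15 = 420 combinations, all inside the lag of 3.6.1.
- Kept by the literal 6.7.1: 28 × 1 = 28, and 28/420 = 6.7%.
- Kept if the limit is applied to onset: 420 of 420. Events with onset on Days 29 to 42 stay out.

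These are counts of permitted days and combinations. They are not shares of calls or of events, because the documents give neither the distribution of call dates nor a post-dose event rate.

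**The case against.** The best reply is that the SAP already means onset. Section 6.7.1 contains the start-date counting sentence, the only event dates it names are start and end dates, and no adverse-event assessment date is defined on which a program could cut. SAP 3.6.1 also works by occurrence. Read together, an event starting on Day 10 and reported on Day 35 is kept.

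As evidence of intent, this stands, and it is why the loss is conditional. It does not remove the conflict. The start-date sentence governs allocation between the open-label and double-blind phases, whereas the 28-day sentence is separate, comes last and covers every analysis in the section. The sponsor data standards to which the section refers are not part of the documents, so they cannot be assumed to settle it.

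The reply also limits what may be claimed. A reader might make several stronger inferences that the documents do not support:
- *That every call is lost.* A call on Day 28 satisfies both rules.
- *That the call is the only post-treatment safety assessment.* Visit 6 is also the early-withdrawal visit and collects adverse events (Protocol 6.2.7). A subject more than 14 consecutive days off drug is discontinued (Protocol 6.3), so that visit can follow the last dose and still fall inside 28 days.
- *That almost all post-dose events disappear.* Volunteered events are reportable (Protocol 8.1, 8.14), unplanned visits are allowed, and serious events go to the sponsor within 24 hours of the investigator's awareness (Protocol 8.15.1).
- *That 28/(168 + 28) = 14.3% of at-risk time is lost in each phase.* Randomized subjects continue treatment at Week 24 and have no post-dose window there. For one who completes 48 weeks the share is 28/(336 + 28) = 7.7%, and even that is a ceiling which assumes that nothing is learned outside the call.
- *That the 28-day limit is itself too short because of the six-week text in Protocol 4.4.2.* The words "may pose a risk during treatment and for 6 weeks following completion of the study" concern household contact with people given live vaccines. They do not define an adverse-event risk window.

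**Conclusion.** The wording of SAP 6.7.1 conflicts with SAP 3.6.1 and should be corrected. On the literal reading, 14 of 15 permitted call days fall outside the cut-off, and events that began on post-dose Day 1 to 28 but were first reported on those days would be dropped.

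This is an inconsistency in the plan, not a demonstrated loss of data. It takes effect only if the programmer treats the assessment as the date of contact. The events exposed are mainly non-serious ones, with any serious event first learned of at the call. Their number cannot be computed from the documents.

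The primary efficacy analysis is untouched. The rule is the same in both randomized arms, so there is no basis here for claiming a bias in one direction between them.

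**What to change.** In SAP 6.7.1, replace the restriction on assessments with one on onset, for example: *these analyses include events whose onset is on or before the 28th calendar day after the final dose of study drug, whatever the date on which they were assessed or reported.*

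This brings 6.7.1 into line with the lag rule in SAP 3.6.1 and with the 28-day serious-event period in Protocol 8.2. Events starting after Day 28 remain outside these summaries, as the lag rule implies.

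The cost is one sentence of SAP text and a matching line in the programming specification. No visit, data collection or clinical rule changes. Reported counts could rise slightly compared with a literal application of the present wording.
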